10.2 Lost to follow-up

Participants will be identified as lost to follow-up if it is not possible to contact them directly or the designated additional contact person for follow-up. At enrolment, participants will be asked to provide details of an alternative contact person (e.g. close friend, relative or carer) whom they are happy for members of the research team to contact for follow-up if the participant themselves cannot be contacted. Participants will also be asked to consent to the research team communicating with their GP if required.

11 Trial intervention

Participants will be randomised in a 1:1:1 ratio to receive an oral course (up to 36 months) consisting of one of the following treatments:

- 1) A 75mg clopidogrel tablet taken once daily
- 2) Dual antiplatelet therapy with a 75mg aspirin tablet and 75mg clopidogrel tablet, both taken once daily
- 3) Dual antiplatelet therapy with a 75mg aspirin tablet taken once daily and a 2.5mg rivaroxaban tablet taken twice daily

Sites are encouraged to prescribe 'best care' concomitant risk factor reduction medication as per NICE guidelines. If indicated, this includes high-dose statin therapy, blood pressure and diabetes control, and smoking cessation help.

11.1 Treatments

All 3 Investigational Medicinal Products (IMPs) are commonly prescribed in primary and secondary care and will be as outlined in section 11.3. The use of generic brands is permitted and trial risk for this is assessed in the CLARITY risk assessment form.

 The Summary Product Characteristics (SmPC) for clopidogrel (dated 08-Jan-2024 as updated by electronic medicines compendium (eMC)) made by Aspire Pharma Ltd will be used as the RSI.

- The SmPC for aspirin (dated 26-Aug-2021 as updated by eMC) made by Dexcel Pharma Ltd will be used as the RSI.
- The SmPC for rivaroxaban (dated 04-Aug-2023 as updated by eMC) made by Bayer plc will be
 used as the RSI.

Updated versions of the RSI will be circulated to sites by email as required by the central trial team at CTR.

11.2 Treatment supply and storage

The IMPs will be sourced from local NHS hospital stock at participating sites and are typically available and stored in the Pharmacy department. These medicinal products do not require any special storage conditions and are stored in clearly labelled containers at room temperature/below 25°C, the conditions specified in the SmPCs. They are stable with a long shelf life under standard conditions (room temperature/below 25°C) therefore, IMP storage temperature will not be monitored in this trial consistent with Type A clinical trials.

11.3 Treatment prescribing and dispensing

Local routine prescribing procedures will be followed for each IMP, for example, the IMP will be prescribed by the participant's treating clinician according to the trial arm allocation and either dispensed by the hospital pharmacy department or a community pharmacy.

Treatment will commence within 10 days post-endovascular intervention.

For inpatient cases, the medication will be administered by ward nurses or other appropriate health care providers in accordance with the relevant SmPC, manufacturer's recommendations and instructions of use. Before discharge, patients will be given clear instructions for use. Once discharged from the hospital, participants will self-administer the allocated IMP.

For day patients/outpatient procedures, participants will be supplied with the IMP as part of routine discharge after the endovascular procedure and treatment will commence at home. If the patient is already in the community after the procedure and at the point of randomisation, primary or secondary care prescribers will be used and stock dispensed from either hospital or community pharmacies depending on local arrangements.

Each dispensed drug supply will vary depending on local arrangements. The post-procedural antithrombotic medication may be prescribed by either vascular surgery or interventional radiology teams. Participants will obtain an additional supply of their prescribed medication from a community pharmacy or secondary care pharmacy depending on the local set-up.

The participant will take the trial medication during the trial duration (up to 36 months). The treating clinician will be responsible for the care of the participant once the participant is no longer in the trial or withdraws from taking the trial medication for any reason.

Participants may continue on the medication after completion of the trial as part of their standard care. Prescribing and dispensing arrangements will not change after the trial has ended.

11.4 Dosing schedule

Standard care peri-procedural antithrombotic medication should be used as per unit preference. The IMP may be started at any time post-procedure at the discretion of the clinician up to 10 days post-procedure. Sites will be encouraged to start the IMP as soon a clinically possible.

Participants will only be permitted to have a single type of antithrombotic regimen for the duration of the trial. Clinically mandated changes to the patient's antithrombotic regimen would usually be secondary to one of the events we are capturing which would truncate the patient in the trial as part of the statistical plan. If there were another reason for a clinically mandated change in antithrombotic medication, for example, a new diagnosis of atrial fibrillation, the patient would be censored the day they start the new medication.

Supply chain issues are not expected for any of the drugs. Changes to trial drugs and reason will be followed-up in the trial (see section 12.2).

Each IMP will be administered orally in tablet form throughout the trial to the following dosing schedule:

Clopidogrel

Dose: 75mg

Dosage Form: Tablet

• Strength of Unit Dose: 75mg/tablet

• Frequency and Timing: Once daily for up to 36 months

Aspirin

Dose: 75mg

Dosage Form: Tablet

Strength of Unit Dose: 75mg/tablet

• Frequency and Timing: Once daily for up to 36 months

Rivaroxaban

Dose: 2.5mg

Dosage Form: Tablet

• Strength of Unit Dose: 2.5mg/tablet

• Frequency and Timing: Twice daily for up to 36 months

Concomitant therapies

All patients should be treated with 'best care' concomitant risk factor reduction medication as per NICE guidelines (29). This includes high-dose statin therapy, blood pressure and diabetic control, and smoking cessation help (30). Patients taking other doses of anticoagulant or antiplatelet medication are excluded by the inclusion/exclusion criteria. Patients being admitted to the hospital during the trial should have thromboprophylaxis (usually with low molecular weight heparin) as per local protocol (see 11.4.1).

11.4.1 Recommendations for patients undergoing subsequent interventional procedures

Patients can temporarily stop trial medication to undergo interventional procedures where standard clinical practice would be to stop trial IMPs. Sites are encouraged to recommence trial medication as soon as clinically possible.

11.5 Dose modification for toxicity

There will be no dose modifications in this trial.

11.6 Management of toxicity and hypersensitivity reactions

Clopidogrel, aspirin and rivaroxaban are licensed medications with rare, very rare/unknown reports of hypersensitivity reactions.

Patients should be evaluated for history or risk of hypersensitivity to the IMPs and monitored for signs of hypersensitivity and toxicity as per routine practice. Investigators should refer to the IMP SmPC for further information.

If hypersensitivity or systemic toxicity is suspected, the trial medication should be stopped immediately and the participant switched to another medication as deemed appropriate by the treating clinician. Intolerances of the IMP will be managed and reported through the treating clinician according to standard procedures.

Severe antiplatelet or anticoagulant toxicity would be considered a SAR and would be reported within 24 hours (see Section 13 on Pharmacovigilance). Participants will be given a card with details of who to contact at the local recruiting site should they experience any serious adverse reactions due to medication toxicity.

11.7 Management of overdose

If a toxic dose of IMP has been ingested, the management and treatment of the overdose should be conducted in accordance with the IMP's SmPC and the usual clinical pathway (section 4.9 Overdose).

An overdose is not an AE and may not result in any noticeable effect on the participant. However, if the participant experiences a serious adverse event (SAE) that the PI considers may be causally related to an overdose, then this must be clearly stated on the SAE form. Any resulting SAE will be reported following standard reporting procedures for SAEs (see section 14 for SAE reporting procedures).

11.8 Pre-medication

The individual unit standard of care antithrombotic, antibiotic and secondary cardiovascular prevention drugs should be used as normal peri-procedurally.

11.9 Prohibited medications and interaction with other drugs

Clopidogrel, aspirin and rivaroxaban have interactions with other medicinal products. For medications known to be contraindicated with the IMPs, concomitant treatment should adhere to precautions outlined in the SmPCs.

NICE recommends the co-prescription of a proton pump inhibitor for patients at high risk of gastrointestinal bleeding being prescribed dual antiplatelet therapy following coronary artery endovascular intervention to reduce this risk (31).

Omeprazole, a widely prescribed proton pump inhibitor, interacts with clopidogrel and may reduce effectiveness. As a result, we recommend that trial patients have a proton pump inhibitor considered with any history or concern about gastrointestinal bleeding. Patients already taking omeprazole or esomeprazole should be switched to lansoprazole or pantoprazole, which are both available in generic form.

Inhibitors of cytochrome P450 co-prescribed with trial medication (clopidogrel or rivaroxaban) should be managed as per local protocol.

Investigators should refer to section 4.5 of the respective drug SmPC for details of interactions with other drugs.

11.10 Permitted concomitant medications

All concomitant medications clinically indicated are permitted.

11.10.1 Trial Restrictions

As per routine practice, people of childbearing age will be advised not to attempt pregnancy whilst taking a Direct Oral Anticoagulant (DOAC) like rivaroxaban. This will be described in the participant information sheet. If they do become pregnant, they will be advised to contact the local team at the recruiting site and this will be managed according to normal clinical practice.

11.11 Accountability procedures

The accountability requirement for this trial is "low -1" and the trial will follow local NHS procedures for the management, dispensing and accountability of the IMPs, with no requirement for CTR accountability, recall and disposal procedures as described in the CLARITY IMP Management Plan.

11.12 Compliance

Compliance/ adherence to the medication will be self-reported by participants through questionnaires at the follow-ups. As this is a real-world, pragmatic trial there are no formal compliance checks such as tablet counting.

11.12.1 Treatment fidelity and adherence:

A combination of methods will be used to effectively assess treatment fidelity. The current medications CRF will be used to document changes and adherence to trial medication. Fidelity will be assessed by:

- Documenting that the correct/allocated IMP is commenced and the timing of IMP initiation post-procedure to ensure it is within the 10 days (see section 11.3).
- Evaluating continuity in treatment for the duration of the trial by examining reports of changes in trial medication and monitoring adverse events or circumstances necessitating a stop to trial medication such as hypersensitivity reactions or pregnancy (see sections 11.6 and 12.1.1).
- For patients who temporarily stop trial medication to undergo interventional procedures, the time to recommence trial medication will also be recorded (see section 11.4.1).

The impact of deviations from the treatment regimen will be analysed as part of the main statistical analysis (see section 15.1, page 53).

- Treatment adherence will be assessed via participant-reported adherence data collected through questionnaires at follow-ups to identify trends or patterns in adherence behaviour, allowing for timely interventions if needed (see section 11.12).
- Intervention adherence and consistency in treatment administration will also be assessed through qualitative process evaluation (see section 12.3), obtaining feedback from participants about their experiences with the medication, including any challenges they face in adhering to the treatment regimen.

Regular monitoring and review of adherence data will be detailed in the CLARITY monitoring plan.

12 Trial procedures

Participants will be recruited over 36 months, and the follow-up period will be variable, with a minimum of 12 months for those recruited at the very end of the recruitment period, and up to 36 months for those recruited early. This is in line with the NICE and European Society of Cardiology (ESC) guidance on dual antiplatelet therapy following acute coronary syndromes in high-risk groups (31,32). All other trial procedures are outlined below.

12.1 Assessments

Outcomes will be assessed at baseline, within 2 months of the endovascular procedure, 6 months and every 12 months post-randomisation (up to 36 months). Data will be collected by the research nurses either in person or via telephone, videocall, email or review of patient records, and entered in electronic format.

The baseline assessments will take place before or within 10 days of the endovascular procedure.

12.1.1 Baseline

The baseline assessment consists of collecting the following information:

- Confirmation of eligibility (by medically qualified doctor)
- Registration
- Medical history
- Endovascular procedure details
- Demographic details including sex at birth, ethnicity
- Presence of rest pain
- Presence of tissue loss
- Participant-reported health-related quality of life (QoL) assessed using EQ-5D-5L and VascuQoL-6

At baseline, participants will be given a contact card providing them with contact details of their local research team. They will be asked to contact the team if there is a change in their medication regimen, specifically when the trial medication is discontinued and replaced with a different medication; they become pregnant; or they experience a major bleeding event, any primary outcomes or an SAE. The contact card will also detail their follow-up appointment schedule.

A letter will be sent to the participant's GP to notify them about the participant's involvement in the trial, the allocated IMP after randomisation, the requirement for repeat prescriptions, and to request the GP promptly inform the local site team of any major bleeding or primary outcome events, SAEs, or interruptions to medication that come to their attention.

Table 2. Schedule of enrolment, interventions and assessments¹

Ass	essment	Source Data	Data type/Measure	Screening	Baseline assessment	Randomisation	Clinical Assessment: 2 months	6 month Follow-up	12 month Follow-up	24 month Follow-up	36 month Follow-up	АР НОС	Responsible for Data Collection	Justification
1.	Informed Consent	Consent form, document ed in medical notes	-	Х									Clinician with delegated responsibility	Consent
2.	Eligibility Assessment	CRF, document ed in medical notes	Inclusion/Exclusion criteria	Х									Clinician with delegated responsibility	Eligibility
3.	(For participants of child-bearing potential) Review of pre-operative pregnancy test result	CRF and document ed in medical notes – eligibility assessmen t	Confirmation of negative pregnancy result	X	-								Site Research team	Eligibility

¹ Taken from the HRA CTIMP protocol template (2016).

Ass	essment	Source Data	Data type/Measure	Screening	Baseline assessment	Randomisation	Clinical Assessment: 2 months	6 month Follow-up	12 month Follow-up	24 month Follow-up	36 month Follow-up	АБ НОС	Responsible for Data Collection	Justification
4.	Randomisati on	CRF	Randomised medication regimen: Dose, Frequency			X							Site Research team	Randomisation
5.	Post-surgery form	CRF/Medic al notes	Revascularisation details: - Treated arteries - Common femoral endarterectomy - Type of endovascular treatment - Antiplatelet loading at the time of procedure - Adjuvants during procedure			X							Site Research team	Randomisation and all outcomes
6.	Registration	CRF	Contact details (inc.Postcode)Alternative Contact detailsGP Contact details		Х								Site research team	Study Management
7.	Demographi cs	CRF	- Age - Sex - Gender - Ethnicity		Х								Site research team	Baseline
8.	Medical history	Medical notes and CRF	- Smoking status - Weight - Alcohol use - Co-occurring conditions		Х								Participant Reported/ Site research team	Baseline

Asse	essment	Source Data	Data type/Measure	Screening	Baseline assessment	Randomisation	Clinical Assessment: 2 months	6 month Follow-up	12 month Follow-up	24 month Follow-up	36 month Follow-up	АД НОС	Responsible for Data Collection	Justification
	6 1	24 1: 1	- Past surgery		.,									2 1: 1
9.	Current Medications	Medical Notes/CRF	- Current medications - Trial medication		X		X	Х	Х	Х	Х			Baseline and Secondary Outcome/ Fidelity of interventions
10.	Details of CLTI	CRF/Medic al Notes	- Rest Pain (yes/no) - Tissue loss (yes/no)		Х								Site research team	Baseline
11.	Health- related Quality of Life	Questionn aire	- EQ-5D-5L - VascuQoL-6		Х		Х	Х	Х	Х	Х	Х	Participant reported	Secondary Outcomes
12.	Composite event-free survival time	CRF/Medic al notes	 - Acute limb ischaemia - Major lower limb amputation - Myocardial infarction - Ischaemic stroke - All-cause mortality 				Х	Х	X	X	X			Primary outcome
13.	Bleeding events	CRF/Medic al notes	ISTH defined major bleeding: - Fatal bleeding - Symptomatic bleeding in a critical area - Bleeding causing a fall in hemoglobin levels (2g/dL or above)				х	Х	Х	Х	Х			Primary safety outcomes

Ass	essment	Source Data	Data type/Measure	Screening	Baseline assessment	Randomisation	Clinical Assessment: 2 months	6 month Follow-up	12 month Follow-up	24 month Follow-up	36 month Follow-up	АД НОС	Responsible for Data Collection	Justification
			- Leading to a transfusion of 2 U or more of whole blood or red cells											
14.	Bleeding events	CRF/Medic al notes	ISTH defined clinically relevant minor bleeding resulting in: - Hospitalisation; - Medical or surgical intervention; - Unscheduled clinical visit/evaluation e.g. telephone/videocall by clinician; - A change in antithrombotic therapy				X	Х	X	X	X			Primary safety outcomes
15.	Bleeding events	CRF/Medic al notes	BARC and TIMI-defined major bleeding including: - Overt bleeding less than type 3 criteria that led to hospitalisation; increased level of care; nonsurgical medical intervention; unscheduled clinical evaluation e.g. telephone/videocall by clinician				х	Х	Х	X	X			Secondary Outcomes

Asse	essment	Source Data	Data type/Measure	Screening	Baseline assessment	Randomisation	Clinical Assessment: 2 months	6 month Follow-up	12 month Follow-up	24 month Follow-up	36 month Follow-up	АБ НОС	Responsible for Data Collection	Justification
			- Required surgical intervention or intravenous vasoactive agents - Cardiac tamponade - Hemoglobin drop related to bleed - Hemoglobin drop amount 3 g/dL and more - Symptomatic bleeding in a critical area - Leading to any transfusion - Probable fatal bleeding - Definite fatal bleeding											
16.	Bleeding events	CRF/Medic al notes	Minor bleeding: Not meeting major bleeding criteria				Х	Х	Х	Х	Х			Secondary Outcomes
17.	Post- Operative	CRF/Medic al notes	Protocol-specified MALE and MACE events including: - Major or minor amputation (trial limb) - Reintervention (trial limb) - Venous thromboembolism - Major amputation (contralateral limb) - Acute coronary syndrome - Ischaemic stroke				х	Х	X	Х	Х			Secondary Outcomes

Asso	essment	Source Data	Data type/Measure	Screening	Baseline assessment	Randomisation	Clinical Assessment: 2 months	6 month Follow-up	12 month Follow-up	24 month Follow-up	36 month Follow-up	AD HOC	Responsible for Data Collection	Justification
			- Recurrent CLTI											
18.	Healing of tissue loss		Healing tissue loss defined as full epithelialisation (yes/no)				X	Х	Х	Х	Х			Secondary Outcomes
19.	Patency following revascularisa tion	CRF/Medic al Notes	- Primary patency of artery (yes/no) - Secondary patency of artery (yes/no)				Х	Х	X	Х	Х			Secondary Outcomes
20.	Reinterventi on rates	CRF/Medic al notes					Х	Х	Х	Х	Х			Secondary Outcomes
21.	Resource Use	Questionn aire / CRF	Client Service Receipt Inventory (CSRI)					Х	Х	Х	Х	Х	Participant reported / Site Research team	Secondary outcome
22.	Qualitative Interviews	Audio recordings										Х		Qualitative/SWAT
23.	SAEs / SARs	Medical notes /CRF										Х	Site Research team	Pharmacovigilanc e
24.	Withdrawal	CRF										Х	Site Research team	Withdrawal

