5.3 Primary outcomes measures

The primary clinical effectiveness endpoint is a composite event-free survival time examined over the trial duration (36 months) comprising:

- Acute limb ischaemia
- Major lower limb amputation
- Myocardial infarction

- Ischaemic stroke
- All-cause mortality

The primary safety outcome is the International Society for Thrombosis and Haemostasis (ISTH) defined major- or clinically relevant non-major bleeding*.

*Clinically relevant non-major bleeding is bleeding that results in hospitalisation, medical or surgical intervention for bleeding, an unscheduled clinical visit, or a change in antithrombotic therapy (24).

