- Remaining intercurrent events: Death is incorporated into the clinical effectiveness primary outcome. Treatment discontinuation is covered by the previous attribute.
- Population-level summary: Hazard ratios, including fixed effects for allocation and random
 effects to model heterogeneity between sites. Regression analysis results will be presented as
 point estimates with confidence intervals and p-values from a log-rank test, and Kaplan-Meier
 curves of cumulative event rates at 36 months (31,32) will be generated to compare arms over
 time.

The primary safety outcome analysis will also use a two-level Cox regression as described above but include only those participants who received at least one dose of their allocated medication ('ontreatment' population). This analysis will include safety events that occurred after receiving the first dose of the trial medication and within 5 days after receiving the last dose.

Secondary outcomes will also be analysed based on ITT (for effectiveness outcomes) or 'on- treatment' populations (for safety outcomes) and using appropriate two-level regression models depending on the type of outcome: Cox regression for time-to-event outcomes, linear regression for continuous outcomes such as QoL measures (allowing for repeated measures where appropriate), and logistic regression for binary outcomes such as reintervention rates.

Table 7. Planned outcome analysis

Outcome	Measure	Analysis	Time frame	
Composite primary	Acute limb ischaemia	Two-level Cox regression		
outcome - Composite event-	Major lower limb amputation	Two-level Cox regression	2m, 6m, 12m,	
free survival time of the following:	Myocardial infarction	Two-level Cox regression	24m and 36m	
the following:	Ischaemic stroke	Two-level Cox regression		

Outcome	Measure	Analysis	Time frame		
	All-cause mortality	Two-level Cox regression			
Primary safety outcome	Major bleeding (ISTH definition)	Two-level Cox regression	2m, 6m, 12m, 24m and 36m		
	MALE (defined as amputation or any major reintervention)	Two-level Cox regression	2m, 6m, 12m, 24m and 36m		
	MACE (defined as recurrent CLTI, amputation affecting contralateral limb, acute coronary syndrome, ischaemic stroke)	Two-level Cox regression			
Caracilar	Major bleeding (BARC definition)	Two-level Cox regression			
Secondary outcomes	Major bleeding (TIMI definition)	Two-level Cox regression			
	Minor bleeding	Two-level Cox regression			
	Primary patency of artery	Two-level logistic regression			

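### The between-visit prompts do not name clinically relevant non-major bleeds, and the participant card does not ask about drug stops without replacement, although the primary safety outcome and its 5-day window depend on both

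*Protocol*

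**What the plan says.** Section 5.3: "The primary safety outcome is the International Society for Thrombosis and Haemostasis (ISTH) defined major- or clinically relevant non-major bleeding". Its footnote defines the non-major part by consequence: admission, treatment for the bleed, an unplanned clinical contact or altered antithrombotic therapy. Table 2 extends unplanned contact to a clinician's telephone or video call and labels the row a primary safety outcome.

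Section 12.1.1 sets the between-visit prompts. Participants are to contact the site if "they become pregnant; or they experience a major bleeding event, any primary outcomes or an SAE", and about a medication change "specifically when the trial medication is discontinued and replaced with a different medication". The GP is asked to "promptly inform the local site team of any major bleeding or primary outcome events, SAEs, or interruptions to medication", so far as these come to the GP's attention.

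The section 13 introduction and 13.2 list the outcome events to be put on the CRF within 24 hours of knowledge. Major bleeding is on both lists; CRNM bleeding is on neither.

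Scheduled contacts fall "within 2 months of the endovascular procedure, 6 months and every 12 months post-randomisation (up to 36 months").

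Section 15.1 restricts the primary safety analysis to participants who took at least one dose: "This analysis will include safety events that occurred after receiving the first dose of the trial medication and within 5 days after receiving the last" (that is, the final intake of trial medication).

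**The concern.** The prompts are narrower than the outcome and the window they feed. A patient who sees a GP about a bleed, is not admitted and carries on has met the primary safety outcome, but nothing on the card plainly tells that patient to call. The card and the letter both list major bleeding beside primary outcomes. A lay reader or GP may therefore take the second term to mean the ischaemic composite.

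The closing date of the window has the same weakness. A participant who stops a trial drug and takes nothing in its place does not meet the card's medication trigger, yet that date decides whether a later bleed counts. Adherence is self-reported at follow-up without tablet counts (11.12).

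Bleeding is the counterweight to any benefit of two drugs over one. Bleeds and stop dates missed during follow-up may not be recoverable at analysis.

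**Working it through.** The protocol states no bleeding rate or capture rate, so there is no figure to reproduce. The check compares the routes by which an event reaches the site, then sizes the exposed follow-up.

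**Routes to the site between visits**

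| Event | Card | GP letter | 24-hour list | Other cover |
|---|---|---|---|---|
| ISTH major bleed | named | named | named | notes |
| CRNM bleed, admitted | yes, as an SAE (Table 3) | yes, as an SAE | not named | notes |
| CRNM bleed, not admitted | only if primary outcomes is read to include it | same | not named | records review (12.1), real-time entry (16.1), next visit |
| Stop with replacement | named | yes, as an interruption | n/a | medication record at each visit |
| Stop without replacement | not named | yes, if the GP learns of it | n/a | medication record at each visit |

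The Table 2 row for CRNM bleeding is ticked at 2, 6, 12, 24 and 36 months, with no ad hoc tick.

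**Gaps between contacts.** Visits at 0, 2, 6, 12, 24 and 36 months give gaps of 2, 4, 6, 12 and 12 months. The mean wait to the next visit is half of each: 1, 2, 3, 6 and 6 months.

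**Follow-up exposed to the 12-month gaps.** Inputs: accrual of 25%, 35% and 40% in years 1 to 3 and dropout of 8% per year (14.3); follow-up capped at 36 months and ending 48 months after recruitment starts (15.1).

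- By hand, without dropout: entrants of years 1, 2 and 3 average 36, 30 and 18 months of follow-up. The mean is 0.25×36 + 0.35×30 + 0.40×18 = 26.7 months. The part after month 12 is 0.25×24 + 0.35×18 + 0.40×6 = 14.7 months. The share is 14.7/26.7 = 55%.
- With exponential dropout at rate −ln(0.92) per year, the shares in the five gaps are 8.2%, 16.1%, 23.3%, 35.2% and 17.2%. After month 12: 35.2 + 17.2 = 52.4%.
- If follow-up instead stops at each participant's last 12-, 24- or 36-month visit (12.2), the last two shares are 31.3% and 12.0%, together 43%.

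These shares count dropout only. Deaths, first bleeds and drug stops would lower the late share.

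**How far capture could fall late (illustration; both inputs are assumptions).** Let c be the share of the affected bleeds found through notes or prompts whatever the gap. Let recall of the rest decay with half-life h, so k = ln 2 / h. Mean capture over a gap of L months is c + (1 − c)(1 − e^(−kL))/(kL). For c = 0.5 and h = 6 months, capture is 0.95 for L = 2 and 0.77 for L = 12, a ratio of 0.81. Capture in a 12-month gap relative to the first 2 months:

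| c | h = 3 months | h = 6 months | h = 12 months |
|---|---|---|---|
| 0 | 0.42 | 0.61 | 0.76 |
| 0.5 | 0.74 | 0.81 | 0.89 |
| 0.9 | 0.95 | 0.96 | 0.98 |
| 1 | 1.00 | 1.00 | 1.00 |

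**Effect on the hazard ratio.** If a fraction q(t) of bleeds at time t is captured, the observed hazard is roughly q(t)λ(t). The observed ratio of two arms is then the true ratio times q_A(t)/q_B(t). Capture common to all arms cancels; capture that differs by arm does not.

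**The case against.** Read literally, the card's mention of any primary outcomes can include CRNM bleeding, because the safety outcome stands under the primary outcomes heading in 5.3. An admitted bleed is an SAE and is prompted on any reading. Table 2 names CRF and medical notes as the source, 12.1 allows records review and 16.1 has sites enter events as they arise. A CRNM bleed by definition has a clinical consequence, so most should leave a record somewhere. GPs are asked about interruptions, and each visit records medication changes with reasons. The card and letter themselves are not shown; 12.1.1 only summarises them.

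Much of this stands, and it confines the point to bleeds managed outside hospital and to unreplaced stops. For those the cover is partial. Real-time entry helps only once the site knows. The stated purpose of access to hospital and GP records is resource-use data (16.4), and community contacts are taken from patient questionnaires supported by a diary (12.2.2). The protocol is also not uniform about the outcome: the follow-up list in 12.2.1 and Table 7 give major bleeding alone.

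A reader might infer that the safety outcome rests on recall, or that late bleeding rates must fall because visits thin out. The documents do not support either. Notes and records are stated sources, and the fall vanishes as c approaches 1.

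**Conclusion.** The prompts and the 24-hour lists omit part of the primary safety outcome, and the card omits stops without replacement although the window runs from the last dose. That follows from the text. Non-hospital CRNM bleeds and last-dose dates may therefore be found late, misdated or missed, more so after month 12 (about 52% of planned person-time, or 43% if follow-up ends at the last scheduled visit).

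The size of the loss is unknown. It depends on how many of these bleeds notes and prompts already find, which the protocol does not say. The likely effect is understated absolute bleeding rates and lower precision. A misdated last dose can move a bleed into or out of the window.

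A reader might also infer that the comparison of regimens is biased. That is not shown: loss common to all arms leaves the hazard ratio roughly unchanged. Capture could differ by arm, because patients and clinicians are unblinded (14.2) and because dropping one of two drugs is possible only in the combination arms. This is a possibility, not a demonstrated bias.

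**What to change.** - Reword the card and GP letter to name (a) any bleed that leads to admission, medical or surgical treatment, an unplanned clinical contact or altered antithrombotic therapy, and (b) any stop of any trial drug, replaced or not, with its date.
- Enter CRNM bleeds on the event CRF as they arise, as for major bleeds.
- Add one sensitivity analysis of the primary safety outcome that counts all bleeds from first dose regardless of stopping, so that one result does not depend on the last-dose date. Its detail can sit in the SAP; the prompts cannot be repaired there.

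The cost is a minor amendment, a few more event forms and one extra analysis. No visits are added, and treatment and its management stay as they are.
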